10.3. Laboratory Evaluations

The hematology, chemistry laboratory analyses, and urinalyses will be performed at a central laboratory. Reference ranges will be supplied and used by the investigator to assess the laboratory data for clinical significance and pathological changes.

Laboratory assessments are performed at Screening, Baseline, Week 4, Week 8, Week 12, Week 16, Week 24 follow-up, Unscheduled Visits and Early Termination Visit.

The following parameters are reported for laboratory data.

- **Hematology:** Hemoglobin, hematocrit, white blood cell (WBC) count (with differential including eosinophils), red blood cell (RBC) count, platelet count, and mean cell volume (MCV).
- Chemistry: Creatinine, aspartate aminotransferase (AST), alanine aminotransferase (ALT), gamma glutamyltransferase (GGT), alkaline phosphatase, lactate dehydrogenase (LDH), total bilirubin, direct bilirubin, creatinine phosphokinase ([CPK], CPK isoenzyme test will be performed only if CPK is elevated to > 2.5 × ULN), albumin, total protein, uric acid, sodium, potassium, calcium, chloride, glucose, urea, total cholesterol, triglycerides, low-density lipoprotein (LDL), and high-density lipoprotein (HDL).

- **Urinalysis:** pH, glucose, ketones, blood, protein, leukocytes, nitrites, bilirubin, urobilinogen, and specific gravity.
- For hematology and chemistry, descriptive statistics by visit and changes from baseline for each
 parameter using the results in standardized international (SI) units will be presented in summary
 tables. Urinalysis parameters will be summarized categorically by visit with percentage based on the
 number of subjects with available data at the visit. By visit summaries will be performed at all visits
 (scheduled visits only) from baseline. Last post-baseline results, minimum and maximum postbaseline values during treatment period will also be included in by visit summary tables.
- Shift tables will be provided for hematology and chemistry by visit (scheduled visits only) and last post-baseline results during treatment period will also be included in the shift tables. Hematology and chemistry results will be classified as low (L), normal (N), and high (H) by the laboratory parameter's normal range. Shift from baseline using low, normal, high will be provided by visit for hematology and chemistry parameters and will also presented for minimum and maximum post-baseline values.
- In addition, summary of hematology, chemistry and urinalysis using potentially clinical significant ranges will be provided by visit. Potentially clinically significant laboratory ranges are presented in section 21 (Potentially clinically significant ranges for laboratory tests).

Distribution of Aspartate Aminotransferase (AST), Alanine Aminotransferase (ALT), Alkaline Phosphatase (ALP), Total bilirubin and Creatinine Phospokinease (CPK) will be displayed graphically with maximum post-baseline values. Also spaghetti plots over time will be displayed graphically for those five parameters.

By-subject listing for subjects with at least one abnormal results (out of reference range) will be provided for hematology and clinical chemistry.

By-subject listing for subjects with at least one potentially clinically significant results will be provided for hematology, clinical chemistry and urinalysis.

All laboratory data will be listed.

10.4. Vital Signs, Height and Weight

Vital signs will include pulse rate, systolic and diastolic blood pressure (after the subject has been sitting for at least 5 minutes), and body temperature.

Vital Signs are performed at Screening, Baseline, Week 1- 2, Week 4, Week 8, Week 12, Week 16, Week 24 follow-up, Unscheduled Visits and Early Termination Visit.

Height will be measured at screening and designated visits; weight will be measured at all visits.

Vital signs, height and weight will be summarized descriptively by visit (scheduled visits only) as continuous variables. Absolute changes from baseline will be included in the summary tables. For vital signs parameters, last post-baseline results during treatment period will be summarized in the table.

Shift from baseline in vital signs using normal, abnormal cs, abnormal ncs results will be provided at post-baseline visits (scheduled visits only) and last post-baseline results during treatment period will be included in the shift table.

In addition, vital signs and weight will be summarized using potentially clinically significant ranges.

By-subject listing for subjects with at least one potentially clinically significant results will be provided for vital signs.

All vital signs, height and weight data will be listed.

Potentially Clinically Significant Ranges for Vital Signs and Weight:

Parameter	SI Units	Potentially Clinically Significant Ranges
Pulse rate	beats/min	< 50 (low) and a decrease > 20 from Baseline or >110 (high) and an increase > 20 from Baseline
Temperature	°C	< 35 (low) or > 38 (high)
Diastolic blood pressure	mmHg	< 50 (low) and a decrease > 10 from Baseline or >90 (high) and an increase > 10 from Baseline
Systolic blood pressure	mmHg	< 90 (low) and a decrease > 20 from Baseline or >135 (high) and an increase >20 from Baseline
Weight	kg	<95% or >105% of change from baseline

10.5. ECG

A 12-lead Electrocardiogram (ECG) will be performed at Screening, Week 16, Unscheduled visit and Early Termination visits.

ECG scan will be reviewed centrally by the designated vendor .

The overall results of the ECGs recorded as 'Normal', 'Abnormal, not Clinically Significant (NCS)' or 'Abnormal, Clinically Significant (CS)' will be summarized by visit (scheduled visits only). And the shift table will be provided.

All 12-Lead ECG data will be listed.

10.6. Physical Examination

A complete physical examination (PE) will include assessments of the head, ears, eyes, nose, throat, neck (including thyroid), skin/integumentary system, cardiovascular system, respiratory system (with respiratory assessment), gastrointestinal system, musculoskeletal system, lymph nodes, and nervous system.

Physical examination are performed at Screening, Baseline, Week 1- 2, Week 4, Week 8, Week 12, Week 16, Week 24 follow-up, Unscheduled Visits and Early Termination Visit.

The assessment results and shift from baseline of the physical examination will be summarized by body system and visit from baseline (scheduled visits only).

Clinically significant respiratory examination findings will be summarized separately.

Abnormal physical examination data will be listed.

10.7. Respiratory Assessment - Spirometry/Peak Expiratory Flow

At screening, the investigator should specifically question all subjects about any medical history of asthma and their respiratory health (eg, wheezing, allergies and infections). All subjects will have spirometry/Peak Expiratory Flow (PEF) performed at screening and baseline. For subjects reporting a medical history of asthma, PEF will be performed at each visit during the clinical trial. For subjects diagnosed with de novo asthma, PEF will be performed at all visits starting with the visit in which the diagnosis was confirmed.

Actual PEF (L/min), Predicted PEF Rate (L/min) and Actual PEF Rate of the predicted value (%) will be summarized descriptively by visit (scheduled visit only) as continuous variables. Absolute change from baseline will also be included in the descriptive analysis.

Also spaghetti plots over time will be displayed graphically for Actual PEF (L/min).

Number of subjects with abnormal PEF (actual PEF < 80% of the predictive value) will be summarized separately.

PEF assessment will be presented in listings.

10.8. Asthma Control Test

Subjects with a medical history of asthma will take the Asthma Control Test (ACT) at each study visit before questioning and physical examination by the investigator. The ACT is a subject-completed assessment consisting of 5 questions. Each question is answered with a score in a range of 1 to 5 and lower score represents the more severe condition. A total ACT score is obtained as the sum of the 5 individual question scores.

ATC score and the change from baseline will summarized descriptively by visit (scheduled visits only) as continuous variables.

Also spaghetti plots over time will be displayed graphically for ACT.

Number of subjects with ACT score ≤ 19 will be summarized separately.

ACT assessment data will be presented in listings.

10.9. Other Safety

Confirmed pregnancy test results, childbearing potential, premense status results, biomarker and virology assessment data will be presented in a listing.

11. Immunogenicity

Blood samples will be collected to assess anti-drug (anti-nemolizumab) antibodies (ADA). Serum samples will be assessed for ADA at Baseline, Weeks 4, 8, 16, 24 and at any unscheduled visit for safety reasons.

Screening ADA, confirmation ADA, ADA titer, nutralizing antibodies, and treatment-related ADA will be will be summarized for the Safety population (scheduled visits only).

A treatment-related ADA is a post-baseline confirmatory ADA sample showing positive results while the baseline sreening or confirmatory ADA sample shows negative results.

All Immunogenicity data will be listed for the Safety population.

12. Health Economics

Not applicable.

13. Interim Analyses

An interim analysis is planned after approximately 10 subjects complete the Week 8 visit. The study will attempt to enrol at least 3 subjects with a low body weight (≤ 61 kg) for the interim analysis and approximately 6 total subjects with low body weight for the overall study population, with investigators attempting to enrol subjects at the lower age range (12-14 years old). The interim analysis will assess whether the observed safety and PK data from adolescents are similar to the data obtained in adults, which is the basis for allowing recruitment of adolescent subjects into the planned nemolizumab Phase 3 studies for AD (pivotal and open-label extension protocols).

Outputs presented for the interim analysis and for the IDMC are marked in Sections 18 (Index of Tables), Section 19 (Index of figures) and Section 20 (Index of Listings). But the selected output list for IDMC meeting can be updated by IDMC member's request.

14. Changes from Analysis Planned in Protocol

No changes to the methods planned in the protocol are foreseen.

15. Reference List

Not applicable.

16. Programming Considerations

All TLFs and statistical analyses will be generated using SAS® 9.4 or higher (SAS® Institute Inc., Cary, NC, USA). Computer-generated table, listings and figures (TLF) output will adhere to the following specifications.

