#### 6.2.2 Immunogenicity

 ADA assessments (screening, confirmatory, NAb), at baseline, Weeks 4, 8, 16, 24 and unscheduled visits for safety reasons

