## 7.4.4 Removal of Subjects From Therapy or Assessments

Although the importance of completing the entire clinical trial will be explained to the subjects, any subject is free to discontinue his/her participation in the study at any time and for whatever reason, specified or unspecified, and without any prejudice. No constraints are to be imposed on the subject, and when appropriate, a subject may be treated with other conventional therapy when clinically indicated. Investigators or the sponsor can also withdraw subjects from the clinical trial if deemed to be necessary.

Subjects may stop study drug for any of the following reasons:

- Subject consent withdrawal
- · Use of non-permitted concurrent therapy
- Non-compliance with the study drug or study schedule
- Lost to follow-up
- Occurrence of AEs not compatible with the continuation of subject participation in the study, in the investigator's opinion, or unacceptable to the subject to continue
- Serious immediate-type allergic manifestations including anaphylactic reaction
- Pregnancy
- Use of systemic rescue therapy during the run-in period through the Week 12 visit (last study drug injection), unless otherwise specified in Table 8 of Section 7.5.8.2.
- Investigator request
- · Intercurrent illness
- Diagnosis of a malignancy (except curatively treated in situ cervical carcinoma or basal cell carcinoma)
- Any opportunistic infection (such as active TB and other infections whose nature or course suggest an immune-compromised status)
- Sponsor request
- Treatment failure

The reason(s) for withdrawal will be documented in the case report form (CRF). Subjects who have been enrolled and treated will not be replaced by another subject.

CONFIDENTIAL Page 45 of 99

Subjects who prematurely discontinue study drug will be encouraged to complete the scheduled study visits.

When a subject discontinues study drug, he/she will be fully assessed whenever possible. Subjects discontinuing study drug before the Week 16 visit should attend an early termination visit and a follow-up/final visit 12 weeks after the last study drug injection for safety follow-up.

Reasonable efforts will be made to contact subjects who are lost to follow-up. These efforts must be documented in the subject's file.

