#### 7.6.2 Unscheduled Visit

The subject should be reminded to adhere to the study schedule. Unscheduled visits are defined as visits to repeat testing for abnormal laboratory results or for follow-up of AEs. Visits occurring outside of the visit window are not considered as unscheduled visits.

blood sample collection for PK and ADA analyses are mandatory during unscheduled visits for safety reasons.

CONFIDENTIAL Page 54 of 99

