# 9.4.2 PK Parameters and ADA Analyses

The PK parameters obtained using modelling techniques will be regarded as primary endpoints for the PK analyses (see details in Section 6.4.1). Primary inference for all the PK parameters will be based on the pharmacokinetic analysis population.

The PKPD relationship between nemolizumab plasma concentrations and the selected clinical outcomes (EASI, IGA and NRS) will be investigated, as appropriate, using a PKPD model development based on previous clinical data.

The pop-PK and PKPD models will be detailed in a separate Modeling Analysis Plan.

The concentration at each time point will be summarized as arithmetic mean, standard deviation, median, minimum, and maximum, number of BLQs (Below the Limit of Quantification).

Descriptive statistics (n, arithmetic mean, standard deviation [SD], minimum, median, maximum) will be calculated for all PK parameters obtained using NCA.

For ADA analyses, the incidence of positive ADA results will be summarized (absolute occurrence, percent of subjects, treatment-related ADA). A presentation of ADA results will be detailed in the SAP.

CONFIDENTIAL Page 74 of 99

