4.2. Immunogenicity Endpoints

 Anti-drug antibody (ADA) assessments (Screening, confirmatory, neutralizing antibody (NAb)), at Baseline, Weeks 4, 8, 16, 24 and Unscheduled visits for safety reasons.

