6.1. General Methods

This section describes analytical analysis issues that relate to all or some of the analytic analysis sections that follow. It describes general guidelines for analysis as well as the following items:

- SAS version 9.4 or higher will be used.
- CCI will be responsible for reporting the demographic, safety, and efficacy data including listings of the administration information for collection of PK and PD samples.
- Unless otherwise specified, summaries will be presented by visit.
- The total number of subjects in the treatment group (N) will be used as the denominator for percentage calculations, unless stated otherwise in the table shell.
- Continuous variables will be summarized using the number of observations (n), mean, standard deviation (SD), median, minimum, and maximum. Categorical variables will be summarized using number of observations (n) and percentages of subjects.
- Subject data listings will be presented with the ITT population for efficacy assessments, with the Safety Population for safety assessments and with the PK population for PK assessments, unless stated otherwise.
- In general, the listings will be sorted by subject number, and assessment date (and time) if applicable.
- Multiple assessments at a given time point (repeat, and unscheduled) will not be included in summary tables unless specified otherwise, but will be included in the listings.

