6.6. Analysis Visit Window

Efficacy by-visit summaries will use the analysis visit. Unscheduled and early termination visits will be windowed based on the following analysis visit window. If multiple measurements are taken within the same window, the one taken closest to the target study day will be used for the analysis. If there are multiple measurements with same difference from target day, the later assessment should be used for the analysis.

		Visit	Window
Analysis Visit	Target Study Day	EASI, IGA, BSA, SCORAD	DLQI/cDLQI
Baseline	1	<=1	<=1
Week 1-2	10	2 to 19	NA
Week 4	29	20 to 42	NA
Week 8	57	43 to 71	NA
Week 12	85	72 to 99	NA
Week 16	113	100 to 141	100 to 141
Week 24 Follow-up	169	> 141	> 141

Daily diary efficacy data (pruritus and sleep disturbance NRS) will be classified into analysis visits as follows considering the data during the 7 days immediately preceding each scheduled visit.

This document is confidential.

SAP Version: Final Version 3.0, 21-Sep-2020

Controlled Document ID: 3903A.01, Effective Date 29-Oct-2018

Filing requirements: TMF

Sponsor: Galderma Research & Development, LLC; Protocol No.: RD.06.SPR.116912, Version 6.0

Analysis Visit	Target Study Day	Diary Data Window
Baseline	1	-7 to -1
Week 1-2	10	3 to 9
Week 4	29	22 to 28
Week 8	57	50 to 56
Week 12	85	78 to 84
Week 16	113	106 to 112
Week 24 Follow-up	169	162 to 168

Daily topical AD medication used data will be classified into visit intervals as follows.

Analysis Visit Interval	Target Study Day	Diary Data Window
Baseline to Week 1-2	10	1 to 9
Week 1-2 to Week 4	29	10 to 28
Week 4 to Week 8	57	29 to 56
Week 8 to Week 12	85	57 to 84
Week 12 to Week 16	113	85 to 112
Week 16 to Week 24 follow-up	169	113 to 168

Safety and pharmacokinetics data will not be windowed for by-visit summary. i.e., scheduled visit data will be used for analysis.

7. Demographic, Other Baseline Characteristics and Medication

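### Unscheduled ECGs that the protocol says will be summarized are left out of the SAP's by-visit ECG table, and ADA positives seen only at unscheduled safety visits are not counted in the ADA summary (minor)

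*SAP*

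**What the plan says.** **ADA.** Protocol 6.2.2 lists as a primary endpoint "ADA assessments (screening, confirmatory, NAb), at baseline, Weeks 4, 8, 16, 24 and unscheduled visits for safety reasons". SAP 4.2 repeats the timing: "at Baseline, Weeks 4, 8, 16, 24 and Unscheduled visits for safety reasons". Protocol 7.6.2 adds that "blood sample collection for PK and ADA analyses are mandatory during unscheduled visits for safety reasons". Protocol 9.4.2 asks for the incidence of positive ADA as a count, as a percentage of subjects and as treatment-related ADA, and then says: "A presentation of ADA results will be detailed in the SAP".

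SAP Section 11 has screening ADA, confirmatory ADA, titer, neutralizing antibodies and treatment-related ADA "summarized for the Safety population (scheduled visits only". It defines treatment-related ADA as a positive confirmatory sample after baseline when the baseline sample was negative, with no limit on visit type. All ADA data are listed.

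**ECG.** Protocol 9.4.3.3 says that ECG change from screening will be summarized for Week 16 and for unscheduled visits. Protocol 6.2.3 and SAP 4.3 define the endpoint with the same two occasions. SAP 10.5 summarizes the overall ECG reading by visit for scheduled visits only, then says in a separate sentence that a shift table will be produced. All ECG data are listed.

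**General rules.** SAP 6.1: "Multiple assessments at a given time point (repeat, and unscheduled) will not be included in summary tables unless specified otherwise". SAP 6.6: "Safety and pharmacokinetics data will not be windowed for by-visit summary. i.e., scheduled visit data will be used for analysis". SAP Section 14 foresees no change from the protocol's methods.

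**The concern.** In both cases the endpoint names a kind of visit that the summary then leaves out, and SAP Section 14 gives the reader no notice of it.

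Unscheduled visits exist to repeat abnormal laboratory tests or to follow up adverse events. ADA samples from them come from subjects in whom a safety question has already arisen. If a subject's only positive sample is one of these, the reported figure for a primary endpoint misses that subject.

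For ECG, Week 16 is the only routine recording after dosing; the schedule has none at Week 24. An unscheduled ECG taken for safety has no other row in a by-visit table limited to scheduled visits.

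**Working it through.** The plan states no figure for this point, so the check is a comparison of texts plus one line of arithmetic.

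**1. ECG**

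| Source | Unscheduled ECGs |
|---|---|
| Protocol 9.4.3.3 | to be summarized |
| Protocol 6.2.3, SAP 4.3 | part of the endpoint |
| SAP 10.5, by-visit summary (Table 14.3.4.3.1) | excluded |
| SAP 10.5, shift table (Table 14.3.4.3.2) | not stated |
| SAP 10.5, listing | included |
| SAP 14 | no change declared |

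The first and third rows conflict, and the last row means the conflict is undeclared. The fourth row is open. For laboratory data (SAP 10.3) and vital signs (SAP 10.4), the SAP attaches the scheduled-visit limit to the shift tables themselves; for ECG it does not. The default in SAP 6.1 concerns several assessments at one time point and does not clearly settle the status of an ECG taken between visits.

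**2. ADA**

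| Source | Unscheduled ADA samples |
|---|---|
| Protocol 6.2.2, SAP 4.2 | part of the endpoint |
| Protocol 7.6.2 | mandatory at safety visits |
| SAP 11, definition of treatment-related ADA | no visit limit |
| SAP 11, summary (Table 14.3.4.5.1) | excluded |
| SAP 11, listing (16.2.8.2.9) | included |

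A subject who is negative at every scheduled ADA visit and confirmed positive at an unscheduled one meets the SAP's own definition but is outside its summary.

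**3. Direction and size**

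Let S be the subjects with a treatment-related positive at a scheduled visit, U those with one at an unscheduled visit, and N the number of subjects.

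- Using all samples: |S ∪ U| / N
- Scheduled visits only: |S| / N
- Difference: |U not in S| / N, which cannot be negative

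So the restriction can lower the any-positive percentage but never raise it. For one such subject:

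- Final analysis, N about 20: 1/20 = 5 percentage points
- Interim, N about 10: 1/10 = 10 percentage points

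For scale, exact (Clopper-Pearson) 95% limits are 0 to 16.8% for 0/20 and 0.1 to 24.9% for 1/20. At the interim they are 0 to 30.8% for 0/10 and 0.3 to 44.5% for 1/10. The SAP plans no interval for ADA incidence.

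**4. Can it happen?**

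It needs one subject in U and not in S. Scheduled ADA samples after baseline fall at Weeks 4, 8, 16 and 24, with none at Week 12. An unscheduled sample may therefore be the only one in the 8 weeks between Week 8 and Week 16. Subjects who roll over to the extension study finish at Week 16 and have no Week 24 sample here. Later scheduled samples will catch many positives but not necessarily all. The documents give no basis for a frequency.

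**The case against.** The strongest reply on ADA is that this is a choice of presentation. The endpoint says when ADA is assessed, not which samples enter a table, and protocol 9.4.2 leaves the presentation to the SAP. Scheduled-only by-visit tables are also this SAP's general practice, and every result is listed. Much of this stands. A reader might infer that SAP Section 11 contradicts protocol 9.4.2; it does not. The mismatch is with the endpoint and with the SAP's own definition. Protocol 9.4.2 does ask for a percentage of subjects, however, and leaving out samples that the endpoint names goes beyond layout.

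The table shells are not among the documents. If Table 14.3.4.5.1 is purely by visit, it gives no subject-level status. A reader might infer that Figure 14.2.3.7, which SAP 9.1 colors by ADA class without a visit limit, will classify subjects differently from the table. That is possible only if the table also assigns subjects to classes, which cannot be seen.

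Four further stronger readings are not supported:

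- **That every unscheduled ECG is excluded from both ECG tables.** This is established for the by-visit table only; the shift-table sentence has no visit limit.
- **That early-termination ADA samples are excluded.** SAP Section 11 does not mention them, and the protocol's schedule gives that visit its own column with an ADA sample. The SAP is silent, not restrictive. In addition, subjects who stop early "should attend an early termination visit and a follow-up/final visit 12 weeks after the last study drug injection for safety follow-up", and ADA is sampled at the follow-up visit.
- **That SAP 10.3 already sets a precedent through its minimum and maximum post-baseline laboratory values.** It does not say that these use unscheduled samples, and it confines them to the treatment period.
- **That the ADA comparison of trough concentrations is invalid.** SAP 9.3 speaks of samples while the title of Table 14.2.3.4 speaks of subject status. That wording should be aligned, but it is a separate, supportive analysis. Any error rate for it would rest on correlations and ADA patterns that the documents do not give.

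**Conclusion.** The point holds and is minor.

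For ECG, the SAP as written departs from protocol 9.4.3.3 in the by-visit table without declaring it, and is unclear for the shift table. For ADA, the summary is narrower than the endpoint and than the SAP's definition of treatment-related ADA, so the percentage of subjects can be understated. The size is 5 points per affected subject at N = 20 and 10 points at N = 10. This assumes that the scheduled-only limit also governs any subject-level figure. The number of affected subjects is unknown and may be zero.

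The impact is limited for three reasons. All ADA and ECG results are listed. Protocol 8.6.10 has clinically significant ECG changes reported as adverse events. The ADA listing and Figure 14.2.3.7 are interim outputs alongside the ADA table, and no stated interim rule uses the ADA percentage. The ECG tables are marked neither for the interim nor for the IDMC.

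**What to change.** **SAP Section 11.** Keep the by-visit table. Add a subject-level row for treatment-related ADA, and one for neutralizing antibodies, counting a subject as positive on any post-baseline sample, unscheduled samples included. State that early-termination samples count. Use the same classification for the colors in Figure 14.2.3.7. If the table shell already has such a row, bring the text into line with it.

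**SAP 10.5.** Include unscheduled ECGs in the summary and shift tables, for example through a worst post-screening row. Otherwise, record the restriction as a change in SAP Section 14.

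**SAP 9.3, wording only.** Make the unit of the ADA comparison (sample or subject) agree with the title of Table 14.2.3.4.

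The cost is a few sentences in the SAP, an added row or two in Table 14.3.4.5.1 and unscheduled ECGs in two tables. No new data or visits are needed.

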9.1. Pharmacokinetic Concentration Presentation

Serum concentration data (unit: ng/mL) will be summarized by visit from baseline to Week 24 using the following statistics: n, arithmetic mean, standard deviation, %CV, geometric mean, %CV geometric mean, median, minimum, maximum, 95% CI of mean and number of BLQs (Below Limit of Quantification). BLQ will be considered as missing and excluded from the descriptive summary.

Individual serum concentration and mean concentration will be plotted by visit on both a linear and semi-logarithmic scale on the PK population (unit for x axis: week). For individual concentration plot, BLQ will be considered as missing. For mean concentration plot, mean concentration not calculated will be considered as missing. In addition, individual serum concentration will be plotted over time with different color for subjects with treatment related ADA+ (ADA- at baseline & ADA + after treatment), ADA + at baseline and ADA- from baseline during the study.

Individual serum concentrations will be listed and BLQ will be listed as BLQ.

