9.3. Pharmacokinetic Parameters Presentation

Estimates of main population PK parameters (Cl/F, Vd/F, Tlag, ka), including inter-individual variability, covariate effects, residual error and their relative standard error (RSE), will be presented in a dedicated PK report.

Individual derived PK parameters at steady state estimated with the popPK model and individual observed PK parameters at steady state calculated with the NCA will be summarized using the following statistics: n, arithmetic mean, standard deviation, geometric mean, %CV, median, minimum, maximum and 95% CI. This descriptive statistics will be calculated CCI.

In addition, the comparison of the average observed trough (C_{trough}) nemolizumab concentration between ADA+ samples and ADA- samples will be performed using ANOVA and the comparison results will be presented.

All PK parameters will be listed by subject.

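### SAP Section 11 counts only treatment-induced antibody as treatment-related ADA, so any baseline-positive subject whose titer rises on nemolizumab would be left out of that count

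*SAP*

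**What the plan says.** The definition is in SAP Section 11 (Immunogenicity): "A treatment-related ADA is a post-baseline confirmatory ADA sample showing positive results while the baseline sreening or confirmatory ADA sample shows negative results". It has two conditions, a negative baseline and a confirmed positive afterwards.

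SAP Section 9.1 applies the same split to the individual concentration profiles. It uses three colour classes: "treatment related ADA+ (ADA- at baseline & ADA + after treatment), ADA + at baseline and ADA- from baseline during the study".

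On what is reported, SAP Section 11 says: "Screening ADA, confirmation ADA, ADA titer, nutralizing antibodies, and treatment-related ADA will be will be summarized for the Safety population (scheduled visits only". It adds: "All Immunogenicity data will be listed for the Safety population". Protocol Section 9.4.2 says that "the incidence of positive ADA results will be summarized (absolute occurrence, percent of subjects, treatment-related ADA" and leaves the presentation to the SAP.

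Immunogenicity is listed among the primary endpoints in Protocol Section 6.2.2: "ADA assessments (screening, confirmatory, NAb), at baseline, Weeks 4, 8, 16, 24 and" unscheduled safety visits. In the SAP indexes, Table 14.3.4.5.1 (ADA and neutralizing antibody) and Figure 14.2.3.7 (profiles by ADA result) are both marked for the interim analysis.

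**The concern.** The label says treatment-related, but the rule captures only antibody that the drug induces in a subject who started negative. It has no place for antibody that was present at baseline and then increased under treatment. The SAP foresees baseline-positive subjects, since it gives them a plot colour, and it plans to summarize titer. The information needed to recognize boosting is therefore among the planned outputs, but neither document says how large a rise matters or where such a subject is counted.

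At stake is one line of a primary-endpoint table and one figure. Both feed an interim look at whether adolescent safety and PK resemble adult data. Without a criterion set in advance, someone reading the listing of an open-label study would decide, after seeing the data, whether a given titer rise is treatment-related.

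**Working it through.** The documents give no ADA rate, baseline prevalence or boosting rate, so there is no planned figure to reproduce. The check has two parts: what the rule does with each kind of subject, and how much that could move the rate.

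**How the rule classifies subjects**

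| Baseline | Post-baseline | Treatment-related under SAP 11? | Class in SAP 9.1 plot |
|---|---|---|---|
| Negative | Confirmed positive | Yes | Treatment-related positive |
| Negative | Negative | No | Negative |
| Confirmed positive | Positive, titer stable | No | Positive at baseline |
| Confirmed positive | Positive, titer rising | No | Positive at baseline |

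The last two rows get the same treatment, and that is the gap. A baseline sample that is positive on screening but negative on confirmation satisfies the definition's alternative wording and counts as negative, so that subject can still qualify. The exclusion applies only to confirmed baseline positives.

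**Size per subject**

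The planned sample size is 20 (SAP Section 3.5), and the interim analysis takes about 10 subjects (SAP Section 13). With all subjects in the denominator:

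- Final analysis: 1/20 = 5 percentage points per boosted subject.
- Interim analysis: 1/10 = about 10 percentage points per boosted subject.
- Example (counts assumed): with two induced and one boosted, the SAP reports 2/20 = 10%. Induced plus boosted is 3/20 = 15%.

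**Sensitivity range**

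Let p be the proportion confirmed positive at baseline and b the probability that such a subject's titer rises on drug. Both are assumptions. The expected number left out is 20 × p × b, and the probability that at least one is left out is 1 − (1 − p·b)^20.

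| p | b | Expected left out | Points on the rate | P(at least one) |
|---|---|---|---|---|
| 0 | any | 0 | 0 | 0 |
| 2% | 10% to 50% | 0.04 to 0.20 | 0.2 to 1.0 | 4% to 18% |
| 5% | 10% to 50% | 0.10 to 0.50 | 0.5 to 2.5 | 10% to 40% |
| 10% | 10% to 50% | 0.20 to 1.00 | 1.0 to 5.0 | 18% to 64% |
| 15% | 10% to 50% | 0.30 to 1.50 | 1.5 to 7.5 | 26% to 79% |

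For the last cell, p·b = 0.15 × 0.50 = 0.075, 20 × 0.075 = 1.5, and 1 − 0.925^20 = 0.79.

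**The case against.** The strongest reply is that nothing is lost. Overall confirmatory incidence, titer and neutralizing antibody are all summarized with baseline-positive subjects included, and every result is listed (Listing 16.2.8.2.9). A boosted subject would be visible. Only a label and a count are missing, and no decision rule in the documents depends on the treatment-related rate. All of that stands, and it keeps the point small. But a titer summary with no within-subject change and no threshold does not say who was boosted, so the label has to be set in advance to be of use.

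A reader might infer more than the documents support:

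- **That the reported ADA response is too low.** Only the treatment-related line can be affected, and only if a boosted subject occurs.
- **That the treatment-related rate is the headline immunogenicity result.** The primary endpoint names screening, confirmatory and neutralizing assessments. Protocol Section 9.4.2 lists treatment-related ADA after absolute occurrence and percent of subjects.
- **That a drug-driven fall in concentration would be blamed on pre-existing antibody.** The figure is descriptive, and its class records baseline status without assigning a cause. The formal trough comparison in SAP Section 9.3, "nemolizumab concentration between ADA+ samples and ADA- samples will be performed using ANOVA", works by sample and does not use the treatment-related definition.
- **That the denominator is fixed at all 20 subjects.** SAP Section 6.1 uses total N unless the table shell says otherwise, and SAP Section 16.2.5.2 gives a different default, subjects with an observation. The shells are not in the documents.
- **That a particular fold rise, such as 4-fold, is the right threshold.** The documents give no titer dilution scheme or assay precision from which to derive one.

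**Conclusion.** The point holds in a limited, conditional form. As written, treatment-related ADA means treatment-induced ADA, and a confirmed baseline-positive subject with a rising titer is classed with stable baseline positives in both the count and the figure. The shortfall equals the number of boosted subjects. Under the assumed ranges (p from 0 to 15%, b from 10% to 50%) it is 0 to 1.5 subjects in expectation, and it may well be zero. The per-subject figures assume that all 20 subjects, or about 10 at the interim, are in the denominator. This is a cheap improvement to a primary-endpoint output and does not threaten the study's conclusions.

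**What to change.** Before database lock, amend SAP Section 11 to split treatment-related ADA into two components:

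- **Induced:** baseline negative, at least one confirmed positive afterwards. Denominator: baseline-negative subjects with at least one post-baseline ADA result.
- **Boosted:** baseline confirmed positive, with a post-baseline titer rise above a fold threshold justified from the ADA assay's dilution scheme and precision. Denominator: baseline-positive subjects with at least one post-baseline ADA result.
- **Total:** either of the above. Denominator: all subjects with a baseline and at least one post-baseline ADA result.

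Report all three in Table 14.3.4.5.1, and state the denominators there so that the two general defaults do not compete. Show boosted subjects as a separate class in Figure 14.2.3.7, with matching wording in SAP Section 9.1.

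No new sample or visit is needed, because titer is already a planned output. The cost is a little more programming and a possibly higher reported treatment-related ADA rate. If nobody is boosted, the treatment-related count does not change and the report can say so.
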